Side effects that are associated with the treatment such as local inflammation due to an inadequately placed or polished restoration, and/or oral lichenoid reactions that are in direct vicinity to the study restoration, will be documented in detail and the patient affected will be excluded from the study. In this case, the restoration will be replaced by another material as soon as possible. In addition, a restoration that fractures due to a mechanical failure of the material will also be replaced as soon as possible. It is possible to have an irreversible pulpitis develop after placement of the restoration, as often times happens during routine dental treatment. In this case, the subject will be excluded from the study and will have to continue with the appropriate treatment at the dental office of their choice at their own expense.

Biostatistical analysis

Study design

The goal of this clinical trial is to show that Venus Pearl (a development based on the material "Venus Diamond", Heraeus Kulzer, Hanau – Germany) has a better score than the commercially available control material (Filtek Supreme XTE, 3M/ESPE, Seefeld – Germany and Filtek Supreme Ultra, 3M/ESPE, USA) for the restoration of class II-cavities. Patients older than 18 who show an interproximal (Class II) carious lesion or an existing defective restoration requiring therapy on premolars or molars will be included.

For the determination of the superior outcomes of both fillings a pre-specified evaluation scheme will be used.

The assessment of the replacement will be performed at four time points (1 week, 6 months, 12 months and 24 months after replacement). For the primary analysis the score will be considered 24 months after the replacement.

The primary endpoint will be a mean score calculated as following: There are three aspects to be assessed: aesthetic, functional attribute and biological parameters. For each aspect there are respectively four categories where each has to be assessed on a scale from 1 to 5. Thereby 1 means clinically excellent, 2 means clinically good and 3 means clinically disappointing. This assessment form is given in FDI World Dental Federation (J Adhes dent 9 (1), 121 – 147 (2007)). For each

patient the points of the 12 different evaluation criteria (four categories in the three parts) will be summed up resulting in a score that ranges from 12 to 60.

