Secondary endpoints are the evaluation of secondary caries, plaque accumulation and gingival reactions and the comparison of the primary score at week 1, month 6, month 12 and month 24 after restoration. Beside this, the single components of the three categories of the primary endpoints will be compared.

Randomization, stratification and blinding

This is an observer-blind clinical trial, e.g. evaluators will not know the given treatment. Restorations will be distributed evenly between the control and the experimental groups using randomization lists.

The application of the two restorative materials is limited to premolars and molars and to achieve a uniform distribution of both tooth types, stratification with the strata premolar and molar will be performed in the randomization process. In addition randomization will be stratified by center.

Randomization will be performed centrally by the Institute of Biometrics to ensure admission before allocation. The randomization will not be based on patients' names, rather than on a scheduled visit, to avoid problems with patients that do not show up for the treatment.

In order to guarantee an objective evaluation at the different time points, the Case Report Form has separate sections for each evaluation, so that the evaluators only use the form for the present examination. Through this method, the evaluator cannot see which assessment he/she gave during previous examinations. These sections will only have the patient number information.

The treatment allocation and the corresponding patient ID will be kept in a separate file that is inaccessible for operators and evaluators.

Description of the primary analysis and key secondary analysis

In the primary analysis the superiority of Venus Pearl will be investigated. Therefore the primary analysis will be conducted on the ITT population, e.g. in all randomized patients. The missing values will be replaced as described below. For the comparison of the scores of the Venus Pearl and Filtek Supreme group an ANOVA will be performed 24 months after restoration. Here, center, tooth type and treatment will be incorporated as covariables. The study is successful if the 95 % confidence interval for the treatment effect (Venus Pearl – Filtek Supreme) is below 0.

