In the secondary analysis, caries (yes/no), plaque accumulation (yes/no) and BOP/ Pocket depths, will be examined with logistic regression models including center and tooth type as independent variables. Sensitivity analysis will be applied using mixed models.

If the study is extended to 4 years, the additional appointments taking place 3 and 4 years after restoration placement (late follow-up) will be evaluated descriptively using the same line as described above for the primary analysis.

Missing values

Missing values may be recorded when patients miss examination appointments. In this case the missing values will be replaced by the "last observation carried forward", where the assessment of the previous examination will be carried over to replace the missing value.

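### The success criterion uses 24-month scores filled by LOCF, which can bias the comparison in either direction, and failed restorations have no stated 24-month score

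*Combined protocol and SAP*

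**What the plan says.** The time point is set in the Study design part of the biostatistical section: "For the primary analysis the score will be considered 24 months after the replacement". Under the description of the primary analysis, "the primary analysis will be conducted on the ITT population, e.g. in all randomized patients", using an ANOVA with centre, tooth type and treatment. On gaps it says: "The missing values will be replaced as described below". One result decides the trial: "The study is successful if the 95 % confidence interval for the treatment effect" (Venus Pearl minus Filtek Supreme) lies below 0. The score runs from 12 to 60 and lower is better.

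The Missing values section names LOCF and explains it as the rule "where the assessment of the previous examination will be carried over to replace the missing value". The only cause it mentions is this: "Missing values may be recorded when patients miss examination appointments". Two readings are possible. Under LOCF as usually understood, a score from any earlier visit, even week 1, can stand at month 24. Under the literal explanation only the month-12 score can, and nothing covers a patient who missed that visit too.

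Three other places bear on the point.
- The paragraph on secondary analysis ends with "Sensitivity analysis will be applied using mixed models" and gives no endpoint, visits or model terms.
- Recruitment of patients has missed visits rebooked by phone and counts a patient as a drop-out after three missed appointments.
- Assessment of restorations excludes patients with certain side effects or irreversible pulpitis, and has fractured restorations replaced. The supplied text gives no 24-month score for these cases.

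**The concern.** A carried score is not a 24-month measurement, yet the ANOVA treats it as one. If restorations deteriorate, an earlier score is on average too favourable, by the amount of deterioration still to come. When that error is larger in one arm, it enters the treatment effect. When it is equal in both arms under no true difference, it cancels. A real difference that grows with time is still shrunk.

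Failures raise a separate problem. Exclusion for a side effect or pulpitis, and replacement after fracture, depend on outcome. The LOCF text does not mention them, although the analysis set is everyone randomised. If LOCF is applied to them, and no examination scored the failure first, the pre-failure score stands and the arm with more failures looks better than it is.

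**Working it through.** **The plan's own figures.** 2 sites × 2 materials × 45 = 180 restorations, 90 per arm, under General information. That split is consistent. No effect size, SD, power, expected trend or dropout rate is given, so there is no planned figure for the effect of missing data to reproduce.

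**Assumptions for illustration.** No true difference; 90 independent restorations per arm; linear worsening over 24 months; dropout random within arm. Central case: worsening 2, SD 3. Range: worsening 1 with SD 5, to worsening 4 with SD 2. The nominal false-superiority rate is 2.5%, one side of the 95% interval.

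**Formulas.** Let p be the proportion lost and g the worsening still to come after the last visit seen: all of it after week 1, half after month 12.
- Bias = −(p_test × g_test − p_control × g_control)
- Variance in each arm = SD² + p(1−p)g²
- SE = √[(variance_test + variance_control)/90]
- False superiority = Φ(−1.96 − bias/SE)

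**Worked case, 20% v 10%, lost after month 12 (g = 1).** Bias = −(0.20 − 0.10) = −0.10. Variances are 9 + 0.16 = 9.16 and 9 + 0.09 = 9.09. SE = √(18.25/90) = 0.450. Φ(−1.96 + 0.222) = 4.1%.

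| Dropout, test v control | Bias | SE | False superiority | Over the range |
|---|---|---|---|---|
| 20% v 10%, after month 12 | −0.10 | 0.450 | 4.1% | 2.9% to 9.2% |
| 20% v 10%, all after week 1 | −0.20 | 0.459 | 6.4% | 3.4% to 19.4% |
| 20% each, test after week 1, control after month 12 | −0.20 | 0.457 | 6.4% | 3.4% to 20.4% |
| 20% each, timing reversed | +0.20 | 0.457 | 0.8% | 0.1% to 1.8% |
| 10% v 20%, after month 12 | +0.10 | 0.450 | 1.5% | 0.1% to 2.1%, this row and the next |
| 10% v 20%, all after week 1 | +0.20 | 0.459 | 0.8% | see row above |
| Equal amount and timing | 0 | – | 2.5% | 2.5% |

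Simulation of LOCF with a t interval (40,000 runs) gave 4.3%, 6.4% and 6.3% for the first three rows.

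**Negative controls.** A second simulation used an ANOVA with centre and tooth type, SD 4 and 4,000 runs. Equal 20% dropout on a 4-point worsening gave 2.6%. No change over time, with 30% v 10% dropout, gave 2.2%. Bias disappears when its conditions are absent.

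**Shrinkage.** If a true difference grows linearly from zero, LOCF keeps 1 − p × (share still to come). At 20% dropout in both arms that is 1 − 0.20 = 80% after week 1, or 1 − 0.20 × 0.5 = 90% after month 12. At 10% it is 90% or 95%.

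**Failures.** If one extra failed restoration in an arm is carried forward from before failure, the arm mean is too low by 4/90 = 0.04 points when one of the 12 items should have gone from 1 to 5. It is too low by 48/90 = 0.53 points when all 12 should have.

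**Check of the alternative.** A repeated-measures model was simulated on nine scenarios: the first three rows at each of the three worsening/SD pairs, 4,000 runs each. It used unstructured covariance, treatment-by-visit means and within-restoration correlation 0.5. False superiority was 2.2% to 2.9% and bias was within 0.01 points. This version had no centre, tooth-type or patient terms, and dropout was missing at random.

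**The case against.** The strongest reply is that nothing in the documents suggests loss will differ by material. The 20% v 10% gap is assumed, and with balanced amount and timing the false-superiority rate is 2.5%. Missed visits are rebooked, so a patient last seen at week 1 has missed three later examinations despite that effort; the week-1 figures are therefore bounds. If patients carry both materials, which Recruitment of patients does not settle, a missed visit removes both and dropout tends toward balance. Halving the gap to 15% v 10% gives 3.2% after month 12 and 4.1% after week 1. Shrinkage of a true effect is conservative for a superiority claim. Mixed models are already named as a sensitivity analysis. All of this stands as a limit on size. It does not remove the mechanism, and the mixed-model sentence leaves the success rule unchanged.

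A reader might infer three stronger things that the documents do not support.
- That LOCF will favour Venus Pearl here. The direction depends on which arm has the more favourable carried scores, and that is unknown.
- That equal dropout rates with unequal timing must raise the false-positive rate. With the timing reversed it falls to 0.8%, and bias is zero whenever p × g matches between arms.
- That failed restorations will keep a good score. An examination may record the failure before replacement or exclusion, and LOCF would then carry the bad score. The cited FDI scheme may also say how failures are scored, so one can say only that the supplied text does not.

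**Conclusion.** The concern holds in conditional form. LOCF feeds the only success criterion. If scores change over time, it biases the 24-month comparison whenever the proportion lost times the change still to come differs between arms. False superiority exceeds 2.5% only when the test arm's carried scores are the more favourable ones; in the reverse case it falls below. With balanced dropout of 10% to 20%, a difference growing linearly from zero keeps 80% to 95% of its size.

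The central illustration is 4.1%, for losses after month 12. It rests on an assumed SD, trend and dropout gap, and on independent restorations. The actual size in this trial cannot be determined from the documents. The missing score for failed restorations is a separate gap, and its effect depends on how those cases are handled. The change should be made because it is cheap and the success rule depends on it; confidence is medium because the size is unknown.

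**What to change.** 1. Make the primary analysis a mixed model for repeated measures on the scores at week 1 and months 6, 12 and 24. Include treatment, visit, treatment-by-visit, centre and tooth type, an unstructured visit covariance within restoration, and a patient random effect. Define success as the 24-month treatment contrast with its 95% interval below 0. Keep LOCF as a sensitivity analysis.
2. Before unblinding, state how a restoration that failed as described in Assessment of restorations is scored in the analysis, and do not fill it from a pre-failure visit. Treat an excluded patient's other restorations as missing.
3. Add a delta or tipping-point analysis for missed appointments, to test departure from missing at random. As a separate check of the failure-scoring rule, give failed restorations the worst score (60) and also run this on ranks, because one such score can move an arm mean by up to 0.53 points.

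**Cost.** Mostly SAP wording. The four scores are already collected, and the plan already lists "the comparison of the primary score at week 1, month 6, month 12 and month 24 after restoration" as a secondary endpoint. A short CRF or protocol line may be needed to record failures between visits. The model assumes missing at random, which outcome-dependent exclusions and replacements break, so items 2 and 3 must accompany item 1. The simulation check covers only a simpler model than the one proposed, and the gain cannot be sized without a dropout rate.
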